***PRGF VS CGF in management of
labial dehiscence around immediate
implants (Comparative study)***

Clinical trial registration: NCT05595772

Document Date: July 30, 2022

Introduction and Review

With the increase in esthetic demand, dental implants have become an indispensable part of modern dental practice. However, with the increasing practice of dental implants; the esthetic outcome is considered as important as the functional and biological outcome. **(Haas et al., 2002)**

Immediate implants have been evolved as the first treatment option in cases of the failed tooth to decrease the time of treatment plan. Immediate implantation at the time of tooth extraction has been associated with significantly higher patient satisfaction (95%) compared to early (84%) or delayed (80%) implant placement. **(Hof M. et al., 2015)**

To obtain an effective esthetic outcome with a single implant-supported restoration in the anterior region, it is crucial to preserve and maintain intact the bone anatomy, as well as the overlying soft tissues. The challenge in treatment is when the labial bone plate presents with a dehiscence type defect stemming from etiologies such as chronic inflammation from a mid-facial vertical fracture affecting the periodontal attachment or severe trauma and chronic infection. **(Sarnachiaro GO et al., 2016) (Fürhauser, R. et al., 2017)**

The compromised esthetic result is anticipated when a 1- to 2-mm vertical deficiency in soft tissue is noted. For defects ≥ 2 mm, soft tissue augmentation should be considered before implant insertion. The keratinized gingival (KG) width on the mid-buccal side of the socket: ≥ 2 , 1 to 2, and <1 mm were defined as adequate, compromised, and deficient, respectively. **(Juodzbalsys et al., 2008)**

The extraction sockets were divided into four groups: Class I, intact soft tissue wall and bone walls; Class II, intact soft tissue wall with the destruction of at least one bone wall; Class III, the recession of all soft tissue walls by ≤ 5 mm; and Class IV, the recession of at least one soft tissue wall by >5 mm **(Cheng et al., 2021)**

It was advocated that the resorption of the socket walls that occurs following tooth extraction must be considered to ensure proper implant placement. Surgical techniques including the use of bone grafting materials as well as using different types of barriers to fill the space around the implants were proposed to maintain hard and soft tissue architecture and to regenerate lost bone in areas of dehiscence and bony defects **(Gaia Pellegrini et al., 2013) (Araujo et al., 2005.)**

One of the most popular techniques is guided bone regeneration (GBR), which entails placing a membrane over the defect to create a secluded space into which osteogenic cells can migrate and remain undisturbed over the exposed part of the implant. Guided bone regeneration (GBR) is frequently used in combination with the installment of titanium implants. The application of a membrane to debar non-osteogenic tissues from interfering with bone regeneration is a key principle of GBR **(Elgali I et al., 2017) (Vijayalakshmi R et al., 2012)**

Membrane materials possess several properties which are amenable to modification. A large number of membranes have been introduced for experimental and clinical verification. third-generation membranes have evolved, which not only act as barriers but also as delivery devices to release specific agents such as antibiotics, growth factors, adhesion factors, etc., at the wound site on a time or need basis to orchestrate and direct natural wound healing in a better way **(Sam G. et al., 2014)**

Numerous studies have explored the suitability of biocompatible materials in regenerative medicine. Platelet concentrates are originated from centrifuged blood and are named according to their biological characteristics, such as platelet-rich plasma, platelet-rich fibrin, and concentrated growth factor **(Ding, Z et al., 2021)**

Platelet concentrates have emerged as innovative autologous blood products that escalate tissue healing and regeneration in regenerative therapy. A common characteristic of these products is their higher than baseline platelet concentration, which ameliorates wound healing and tissue repair. Indeed, because these concentrates are autologous, all the biocompatibility issues are avoided **(Chou T-M et al., 2020)**

Platelets have been identified as a manufacturer of high quantity of growth factors, such as Platelet-Derived Growth Factor (PDGF), Transforming Growth Factor-B1 (TGF), TGF-B2, Fibroblast Growth Factor (FGF), Vascular Endothelial Growth Factor (VEGF), Insulin-like Growth Factor (IGF) that invigorating cellular proliferation, matrix remodeling and neo-angiogenesis **(Pakyari, M et al., 2013)**

Four major categories of products can be simply defined, based on their leukocyte content and fibrin architecture: pure platelet-rich plasma, such as Cell Separator PRP or Anitua' PRGF; leukocyte- and platelet-rich plasma (L-PRP), such as PCCS or Ace PRP; pure platelet-rich fibrin (P-PRF), such as Fibrinet PRFM; and leukocyte- and platelet-rich fibrin (L-PRF), such as Choukroun's PRF. **(Chou T-M et al., 2020)**

Plasma rich in growth factors (PRGF), a subtype of P-PRP (pure platelet-rich plasma), is a supernatant enriched in plasma and platelet-derived morphogens, proteins, and growth factors. PRGF represents a complex pool of active mediators that may stimulate and accelerate tissue regeneration, which is generally safe to use and economical to obtain. Autologous PRGF has been approved for clinical use by the European Community and the U.S. Food and Drug Administration (**Anitua et al., 2014**) (**Dohan Ehrenfest et al., 2009**)

The drawback of PRP is its complex preparation process: several procedures are needed to segregate it and it has to be activated by thrombin and calcium chloride. (**Chen, X et al., 2018**)

CGF (concentrated growth factor), the third-generation platelet concentrate presented by Sacco in 2006 carries more growth factors and has a firmer fibrin structure than first-generation PRP and second-generation PRF (platelet-rich fibrin) . Sacco's membrane (CGF) shows a complex three-dimensional architecture which makes it a biomaterial rich in fibrin platelets, leukocytes, and growth factors - very satisfactory both for patient and operator (**Dohan et al., 2006**) (**Chen, X et al., 2018**)

In comparison with previous generations of platelet enrichment, the preparation of CGF membranes does not need additional reagents to generate platelet activation or fibrin polymerization and is less likely to develop immune responses or cross infections (**W. M. Talaat et al., 2018**)

Aim of the study

- Assess the effectiveness of PRGF and CGF in the management of buccal dehiscence and marginal bone level around the immediate implant.
- Compare the effectiveness of PRGF Vs CGF.

Patients and Methods

Patient selection

this study will be conducted on 20 patients indicated for immediate implant placement in the maxillary anterior region. After approval from the ethical committee, the entire patients will be recruited from the outpatients' clinic of the Oral Medicine, Oral Diagnosis, and Periodontology Department. Faculty of Dentistry, Minia University.

Inclusion criteria:

1. Selected patients of both sexes are 20-40 years old.
2. Patients are systemically healthy based on questionnaire dental modification of Cornell index.
3. Gingival health according to the new classification system (2017)
4. The recipient site of the implant is free from any pathological conditions.
5. Class II extraction socket according to Chang's classification system
6. Adequate interocclusal space to accommodate the available restorative components.
7. Adequate native/apical bone to achieve primary implant stability.

Exclusion criteria:

1. Pregnant female.
2. Parafunctional habits such as bruxism and clenching Patients suffering from periodontitis.
3. Smokers.

Ethical regulation and Informed consents

All patients will undergo an immediate implant placement and the complete treatment plan will be explained to all patients including detailed steps, risks, and expected results. Verbal and written informed consent will be obtained from all patients before the commencement of the study. All steps will be examined and approved by the appropriate ethics committee and have therefore been performed following the ethical standards laid down in the Declaration of Helsinki and the research ethics committee of the Faculty of Dentistry, Minia University.

Pre-surgical phase

1. All selected patients will be screened by comprehensive periodontal examination and full periodontal charts will be obtained. A preoperative cone-beam computed tomography (CBCT) will be performed for each patient who met the inclusion criteria before the surgery to determine bone height and width and decide the implant length and diameter to be placed and to evaluate the underlying bone condition.

Randomization

The study will use simple randomization to allocate patients into 2 groups, each group will be included 10 patients.

Group A: (concentrated growth factor group)

ten patients indicated for immediate implant in the maxillary anterior region (class II socket), will be a candidate for immediate implant placement with CGF combined with xenogeneic bone graft

Protocol for CGF preparation:

10 ml venous blood samples will be drawn from the patients and placed in a centrifuge tube without anticoagulants. Then the tubes will be placed in the centrifugation device in an opposing balanced manner and rotated in four sequential steps. The first step at 735 g ($2249 \approx 2200$) for 2 min., the second one at 580 g ($1998 \approx 2000$) for 4 min., the third one at 735 g ($2249 \approx 2200$) for 4 min. and the fourth one at 905 g ($2495 \approx 2500$) for 3 min. The result was a clot that was collected using a straight tweezer and ready to be used

Group B: (platelet-rich in growth factor group)

Ten patients who indicated immediate implant in the maxillary anterior region (class I or class II socket), will be a candidate for immediate implant placement with PRGF combined with xenogeneic bone graft.

Protocol for PRGF preparation:

30 ml venous blood will be collected from the patient then deposited in 5 mL tubes containing sodium citrate anticoagulant. Then the tubes will be centrifuged at 580 G (2270 rpm) for 8 minutes at room temperature. After centrifugation, the blood sample will be layered into the following four distinctive layers:

- 1) 0.5 mL Plasma poor in growth factors (PPGFs) = F1 in the uppermost part of the tube
- 2) 0.5 mL Plasma with growth factors (PGFs) = F2
- 3) 0.5 mL (PRGF) = F3 located immediately above the red blood cell portion in the tube
- 4) Red blood cell concentrate layer

From all tubes, The 500 μ L PPGF will be eliminated and the PRGF will be separated with 500 μ L pipettes and transported to an independent dish then activated using 50 μ L of 10% calcium chloride for every 1 ml of preparation and mixed with xenogenic bone graft then it will be incubated for 40 minutes in 37°C to produce easy to handle gelatinous layer (PRGF) fibrin mixed with the xenogenic bone.

Surgical Phase

1. The surgical site will be prepared by scrubbing the surgical site using Betadine: Povidone-iodine, 7.5% (0.75% available iodine) the Nile Comp. for Pharmaceuticals and Chemical Industries, Alexandria, Egypt
2. Nerve block or infiltration anesthesia will be administrated Articaine (4%) with epinephrine (1:100,000 or 1:200,000)
3. Atraumatic extraction of the tooth or remaining root using periotome, then sequential implant drilling accompanied by copious irrigation will be carried out. then cover screw attached to the implant top by the aid of its driver
4. A sample of venous blood will be withdrawn from the patient and centrifuged without delay according to the preparation protocol of each group.
5. Then the membrane loaded with the bone graft will be applied and condensed around the dental implant filling the gap between the fixture and the walls of the socket.
6. Finally, Tension-free Closure of the wound was achieved using 4/0 vicryl sutures.

Postoperative instructions

1. Routine verbal and written postoperative instructions for periodontal surgery will be given to all patients including ice compression on the surgical site during the first 4 h, a liquid and/or soft food diet for 3 days.
2. As with all surgical procedures, patients will be informed to contact our clinic if any problems will be developed during the postoperative period.
3. The postoperative medications prescribed will be (Amoxicillin+ clavulanic acid*625mg for 7 days) every 8 h or clindamycin** 300 g every 12 h for 7 days for patients allergic to penicillin, and (Ibuprofen*** 600 mg every 12 h for 5 days).
4. The sutures will remain in situ for 2 weeks.

Clinical assessment:

All patients included in the present study will be followed carefully and monitored to motivate the patient for oral hygiene instructions and maintenance of good oral hygiene.

*Augmentin®, GlaxoSmithKline

** Dalacin C®, Pfizer

*** Brufen®, Abbott

Radiographic evaluation

A periapical film with the paralleling technique will be used immediately after the implant placement

And after 9 months CBCT imaging will be used to evaluate:

1- Bony density

2- Marginal bone level.

Statistical analysis:

-All data will be tabulated and analyzed by statistical method.

References

- Araújo, M. G., & Lindhe, J. (2005). Dimensional ridge alterations following tooth extraction. An experimental study in the dog. *Journal of clinical periodontology*, 32(2), 212–218.

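### The dehiscence part of the aim has no defined outcome and no baseline measurement, and the entry rules do not secure a labial defect in either arm

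*Combined protocol and SAP*

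**What the plan says.** **Question.** The title concerns "labial dehiscence around immediate" implants. The first item under Aim of the study is to "Assess the effectiveness of PRGF and CGF in the management of buccal dehiscence and marginal bone level around the immediate implant". The second is to "Compare the effectiveness of PRGF Vs CGF", with no endpoint attached.

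**Entry.** Inclusion criterion 5 requires a "Class II extraction socket according to" a cited classification. The Introduction summarises that classification as "Class II, intact soft tissue wall with the destruction of at least one bone wall", and the class before it as "Class I, intact soft tissue wall and bone walls". Group A is described as "ten patients indicated for immediate implant in the maxillary anterior region (class II socket"). The matching sentence for Group B allows either class I or class II.

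**Measurement.** The preoperative CBCT (Pre-surgical phase) is taken in patients who have already met the inclusion criteria. It serves implant planning and a general view of the bone. The image at placement is a periapical film. The 9-month image is a CBCT, used for two items: bone density and "2- Marginal bone level". The Clinical assessment section covers follow-up and oral hygiene only. The Statistical analysis section is one general sentence and adds no outcome.

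**The concern.** The defect that gives the trial its title is not tied to any measurement. The aim lists dehiscence and marginal bone level side by side as two targets, so the second cannot simply be taken as the measure of the first. If no one records the labial defect before surgery and at 9 months in the same way, the trial cannot say whether it closed or which product closed it better. Neither a larger sample nor a better analysis can recover a measurement that was never taken.

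The entry rules add a second problem. A patient whose labial plate is intact has no dehiscence to repair and so contributes nothing to that question. If such patients may enter one arm but not the other, the arms also differ at baseline in the very feature under study. With 10 patients per arm there is little room for either.

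**Working it through.** The documents give no effect size, SD, significance level or power, so there is no figure of the plan to reproduce. The check is to set the sections side by side.

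**1. Aim against outcomes**

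| Target in title or aim | Outcome listed at 9 months | Baseline specified |
|---|---|---|
| Labial/buccal dehiscence | None named | None: the preoperative CBCT has no defect measurement |
| Marginal bone level | Yes, with no site, landmark or plane | Periapical film at placement; use as baseline not stated |
| (not in the aim) | Bone density | None stated |

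I read labial and buccal as the same surface, since all sites are maxillary anterior. Mesial and distal readings alone would satisfy the wording of the marginal bone level item. The periapical film cannot supply a labial baseline, because it is two-dimensional and does not show the height of the labial plate.

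**2. Aim against entry**

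| Source | Socket allowed | Is a labial defect guaranteed? |
|---|---|---|
| Inclusion criterion 5 | Class II | No: some wall must be lost, but none is named and no minimum size is set |
| Group A | Class II | No, for the same reason |
| Group B | Class I or II | No: Class I has all bone walls intact |

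No other inclusion or exclusion criterion mentions the labial plate. The Group B text contradicts both criterion 5 and Group A. It also cannot work alongside randomization as it stands: eligibility is fixed before allocation, so a socket class cannot be eligible for one arm only. Either the Group B text is not operative, or the two arms are drawn from different populations.

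**3. Illustration of dilution (all inputs are assumptions)**

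Take a two-sample t test with 10 per arm, two-sided 5%, and a true difference d = 1.325 SD in patients with a labial defect. This d is chosen because it gives 80.0% power. Let a share f in each arm have no labial defect and no product difference. The average effect becomes d × (1 − f).

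- f = 0.2: 1.325 × 0.8 = 1.06 SD, power 61.1%
- f = 0.4: 1.325 × 0.6 = 0.795 SD, power 39.1%

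These hold the SD at 1. If the effect sits in one arm only, mixing raises the pooled variance to [2 + f(1 − f)d²]/2:

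- f = 0.2: (2 + 0.16 × 1.756)/2 = 1.140; effect 1.06/√1.140 = 0.993 SD; power about 56%
- f = 0.4: (2 + 0.24 × 1.756)/2 = 1.211; effect 0.795/√1.211 = 0.723 SD; power about 33%

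The documents supply neither f nor d, and the calculation presumes a dehiscence outcome that the plan does not yet have. It also treats the arms alike, whereas the Group B text would make them unequal. It shows direction only.

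**The case against.** **Marginal bone level is in the aim and is measured.** This stands. A reader might infer that the trial cannot answer its question at all. The documents do not support that: one of the two targets in the first aim has an outcome. The gap is confined to dehiscence.

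**A CBCT is three-dimensional, so marginal bone level could be read on the labial side.** This stands in part. The text is silent on site, so it would go too far to say that neither listed outcome can capture the labial bone. But nothing requires a labial reading, and even a labial level at 9 months would have no specified baseline defect to compare with.

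**The intended defect is clear from the title, the Introduction and the aim, and the class definition is a one-line summary of a source not reproduced in full.** This is fair as to intent. Nothing shows that sockets with an intact labial plate will in fact be enrolled. But intent is not an entry criterion, and the explicit admission of Class I in Group B points the other way.

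**The power loss has no anchor in the documents.** This stands in full. The graft is also packed around the whole gap between implant and socket walls, so a product difference at non-labial defects cannot be ruled out. The finding does not rest on those figures.

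**Conclusion.** The concern holds for the dehiscence part of the aim. A stated aim, and the subject of the title, has no defined outcome and no baseline measurement, so the plan followed exactly need not produce an estimate of dehiscence repair in either arm. Entry does not secure a labial defect, and the socket classes contradict each other between criterion 5, Group A and Group B.

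In size, one of the two targets in the first aim is left without an outcome. No defensible loss of power can be quoted, because the share of sockets without a labial defect is unknown. The conclusion rests on reading the class definitions as the Introduction prints them, and on taking the 9-month list as the full set of outcomes. It should be put right before enrolment, because a baseline defect measurement must be planned before surgery.

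**What to change.** **Outcome.** Add as the main outcome the labial bone defect at mid-labial: its vertical height, with labial bone thickness as supportive. Measure it on the preoperative and 9-month CBCTs by the same method, from a landmark present on both scans, such as a fixed anatomical reference or the adjacent teeth. The implant platform will not serve, because it does not exist on the preoperative scan. Compare the arms on the 9-month value with adjustment for baseline (analysis of covariance). Keep bone density and marginal bone level as secondary outcomes, and state the site for the latter.

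**Entry.** State in criterion 5 that the destroyed wall includes the labial wall, confirmed on the preoperative CBCT before randomization. Reconcile criterion 5, Group A and Group B so that both arms have the same socket eligibility; amending criterion 5 alone would leave the Group B text standing.

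**Alternative.** If this is not done, narrow the title and aim to marginal bone level and bone density.

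**Cost.** Protocol wording and a few extra linear measurements; both scans are already planned. Eligibility becomes slightly narrower. Because the CBCT now follows inclusion, using it to confirm eligibility means that some patients will be scanned and then not enrolled. The baseline scan also precedes extraction, so any change in the labial wall at extraction would not be captured.

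### Aim 1 promises the effectiveness of each concentrate, but with xenograft plus a concentrate in both arms and no concentrate-free comparator, only the CGF-versus-PRGF difference can be estimated

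*Combined protocol and SAP*

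**What the plan says.** The section Aim of the study lists two aims. The first is to "Assess the effectiveness of PRGF and CGF in the management of buccal dehiscence and marginal bone level around the immediate implant". The second, listed separately, is to "Compare the effectiveness of PRGF Vs CGF".

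Patient selection gives the total: "this study will be conducted on 20 patients indicated for immediate implant placement in the maxillary anterior region". Randomization gives the arms: "The study will use simple randomization to allocate patients into 2 groups, each group will be included 10 patients". A Group A patient "will be a candidate for immediate implant placement with CGF combined with xenogeneic bone graft"; a Group B patient "will be a candidate for immediate implant placement with PRGF combined with xenogeneic bone graft". No graft-only, no-graft or other concentrate-free group appears anywhere, and no historical or external comparator is named.

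Radiographic evaluation lists two outcomes on the 9-month CBCT, bony density and marginal bone level. Statistical analysis is a single sentence that names no test, significance level, power, effect size, SD or margin.

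**The concern.** Because comparison has its own aim, the first aim reads as a statement about what each concentrate achieves in its own right. The design has nothing against which to judge that. Every patient also receives a xenogeneic graft, an immediate implant and 9 months of healing. The plan's own Introduction describes grafting materials as a means of regenerating lost bone at dehiscence sites, so good results with graft alone are plausible on its own rationale.

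At stake is what the trial may conclude. A report that follows aim 1 as written would state that PRGF and CGF are effective, with no data that separate them from the graft. If the between-arm comparison were also non-significant, nothing in the plan says how to read it, and it could be taken to mean that the two products are equally good.

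**Working it through.** **1. What the arms can identify.** Write G for the combined contribution of xenograft, implant placement and healing, C for what CGF adds and P for what PRGF adds. From the two group descriptions:

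- mean of Group A = G + C
- mean of Group B = G + P
- A − B = (G + C) − (G + P) = C − P

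There are two observable means and three unknowns. Replacing G by G − k, C by C + k and P by P + k leaves both means unchanged for any k. The data therefore fix C − P but not C or P, and more patients do not change this. The presence of G in both arms is not itself the fault: a common G is what makes A − B a valid contrast. Aim 1 fails because no group has G without a concentrate.

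**2. Whether a before-after reading helps.** The Pre-surgical phase section says: "A preoperative cone-beam computed tomography (CBCT) will be performed for each patient who met the inclusion criteria before the surgery". Its stated purpose is planning and evaluating the underlying bone, but it could serve as a baseline for some measures. Change from it to 9 months still equals G plus the concentrate's contribution. Marginal bone level around an implant has no value before the implant exists. As Radiographic evaluation reads, the image immediately after placement is a periapical film and the 9-month image is a CBCT, so that pair is not like for like.

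**3. Precision of the contrast that remains.** The plan gives 10 per group and no calculation, so there is no stated figure to reproduce. The following are assumptions: two-sided 5%, unadjusted two-sample t-test, equal SDs, 10 analysed per arm, and effects in SD units because no SD is given.

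- Degrees of freedom: 10 + 10 − 2 = 18. Standard error of the difference: √(2/10) = 0.447 SD.
- 95% CI half-width: 2.101 × 0.447 = 0.94 SD. An observed difference of that size has p = 0.05.
- Power from the noncentral t distribution with 18 df:

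| True difference (SD) | Power |
|---|---|
| 0.5 | 18% |
| 0.8 | 40% |
| 1.0 | 56% |
| 1.32 | 80% |
| 1.53 | 90% |

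**4. How the assumptions move these figures.** A baseline covariate with correlation r to the outcome multiplies the difference needed by about √(1 − r²), ignoring the lost degree of freedom. From 1.325 SD, r = 0.3, 0.5 and 0.7 give about 1.26, 1.15 and 0.95 SD. Dropout works the other way. With 8 analysed per arm (an illustration; 14 df), the half-width is 2.145 × √(2/8) = 1.07 SD.

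**5. Socket class.** Step 1 needs G to have the same expected value in both arms. Inclusion criterion 5 and the Group A description specify class II sockets, but the Group B description admits "class I or class II socket". The Introduction defines class I as having intact bone walls and class II as having at least one destroyed. If the arms were drawn on different criteria, then A − B = (C − P) + (G_A − G_B), and the second term is unknown.

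**The case against.** The strongest reply is that aim 1 need not be read as a causal claim about each concentrate. It speaks of management of a defect, the title calls the work a comparative study, and the head-to-head comparison is already stated. On that reading aim 1 only describes how each regimen performs, and the plan never names an effect over graft alone. This reading is possible and is the one the design can serve. But the aim names PRGF and CGF rather than their combination with graft, and it uses the word effectiveness, so the wording should be brought into line with it.

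Several stronger readings are tempting but not supported:

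- A reader might infer that the plan intends before-after tests or an equivalence claim. It specifies neither. The criticism is that nothing rules them out.
- A reader might infer that the trial cannot detect a difference below about 1.3 SD. That figure is where power reaches 80%. Smaller true differences are sometimes found (56% power at 1.0 SD), and an observed difference of about 0.94 SD reaches p = 0.05.
- A reader might infer that the randomized comparison is lost as well. It is not. It remains estimable, provided the socket-class statements are reconciled.

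It is also fair to say that the missing comparator and the low precision are separate matters. The first makes aim 1 unanswerable at any size. The second governs only how a result under aim 2 may be read.

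**Conclusion.** The point stands in this form: aim 1, as written, cannot be answered. No effect of PRGF or of CGF can be separated from graft, implant placement and healing, because every patient receives all of them together with a concentrate. This follows from the make-up of the two groups and needs no numerical assumption.

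Aim 2 can be estimated but with wide uncertainty. Under the assumptions in the working, an observed difference of zero would be compatible with nearly 1 SD in either direction. With no margin stated, it could not support a claim that the products are equally effective. Without an SD in the plan, these figures cannot be turned into millimetres or density units.

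**What to change.** - Reword aim 1 as: *To describe 9-month outcomes with CGF plus xenograft and with PRGF plus xenograft.* State that within-arm results are not evidence that either concentrate works.
- Keep aim 2 as the only comparative inference, on the outcomes already listed under Radiographic evaluation (bony density and marginal bone level). If buccal dehiscence stays in the aim, list how it is measured on the CBCT already planned, because it is not among the listed outcomes.
- In Statistical analysis, commit to reporting the between-arm difference with its 95% CI, and state that a non-significant result will be called inconclusive, not equivalence. Give the precision figures with their assumptions.
- Reconcile inclusion criterion 5 and the Group A and Group B descriptions on socket class.

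The cost is a less ambitious stated aim, plus a measurement definition if dehiscence is kept. No extra patients or arms are needed. Keeping aim 1 as a claim about each concentrate would cost far more. As an illustration, take a graft-only third arm, two comparisons each at two-sided 2.5%, 80% power and a difference of 1.0 SD. That needs 21 per arm, or 3 × 21 = 63 patients.

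### Simple randomisation of 20 patients gives the stated 10 per group only 17.6% of the time; the scheme that would enforce 10/10 is not named and no concealment is described

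*Combined protocol and SAP*

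**What the plan says.** Patient selection sets the total: "this study will be conducted on 20 patients indicated for immediate implant placement in the maxillary anterior region". The Randomization section then gives the method and the group sizes together: "The study will use simple randomization to allocate patients into 2 groups, each group will be included 10 patients". The Group A and Group B descriptions each repeat the figure of ten.

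Nothing else is said about allocation. The protocol has no block or other restricted scheme, no rule for reaching 10/10, no account of who makes or holds the sequence, no concealment step, no stated time of allocation, and no blinding of operator, patient or assessor.

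The arms are easy to tell apart in the operating room. For CGF, "10 ml venous blood samples will be drawn from the patients and placed in a centrifuge tube without anticoagulants". For PRGF, "30 ml venous blood will be collected from the patient then deposited in 5 mL tubes containing sodium citrate anticoagulant". The arm-specific work begins at step 4 of the Surgical Phase: "A sample of venous blood will be withdrawn from the patient and centrifuged without delay according to the preparation protocol of each group".

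**The concern.** Simple randomisation means that each patient is allocated independently of the others, so the group sizes are random. A fixed 10 per group means that they are not. Staff following this text would have to improvise a rule to reach 10/10, and the properties of that rule would be unknown to any reader of the results.

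Any rule that ends at exactly 10/10 makes at least the 20th allocation certain to someone who knows the first 19. The operating team would know them, because the blood volume, tubes and processing differ by arm. With no concealment described, nothing in the plan prevents other allocations from being known early as well.

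Foreknowledge matters because entry depends partly on judgement, for example on whether there is enough native bone for primary stability. With 10 per arm, two steered patients are 20% of an arm, and the Statistical analysis section gives no method that could address the resulting bias. The exposure is greater because the socket classes do not agree across the document. Inclusion criterion 5 and Group A name class II only, while Group B names class I or class II. Those passages must be reconciled.

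**Working it through.** **Inputs.** Total N = 20 (Patient selection). Two groups of 10 by simple randomisation (Randomization; repeated under Group A and Group B). The 1:1 ratio is implied by the equal sizes. It is also the most favourable assumption, since p = 0.5 maximises the chance of 10/10.

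**The plan's own figure.** The plan gives no effect size, standard deviation, alpha or power, so the 20 cannot be re-derived. The 10 per group is 20/2, which under simple randomisation is only the expected group size. Its standard deviation is √(20 × 0.5 × 0.5) = 2.24.

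**Chance of the stated sizes.**

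- P(10/10) = C(20,10)/2^20 = 184756/1048576 = 0.1762.
- P(9/11 or closer) = (184756 + 2 × 167960)/1048576 = 520676/1048576 = 0.4966, so P(8/12 or more uneven) = 50.3%.
- Adding the 8/12 splits: (520676 + 2 × 125970)/1048576 = 772616/1048576 = 0.7368, so P(7/13 or more uneven) = 26.3%.

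**Certain allocations if 10/10 is enforced.** Let T be the number of final allocations fixed once one arm holds 10 patients. The protocol does not state the mechanism, so two are shown.

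- *Coin until one arm is full:* P(T = t) = 2 × C(19−t, 9)/2^(20−t), for t = 1 to 10. The mean is 20 × C(20,10)/2^20 = 3.52.
- *Shuffled list of ten A and ten B:* P(T = t) = 2 × C(19−t, 10−t)/C(20,10), for t = 1 to 10. The mean is 2 × 10/11 = 1.82.

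| Mechanism | Mean T | P(T ≥ 2) | P(T ≥ 4) |
|---|---|---|---|
| Coin until one arm is full | 3.52 | 81.5% | 45.4% |
| Shuffled 10/10 list | 1.82 | 47.4% | 8.7% |

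T is at least 1 under both.

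**Cost of imbalance if it is left alone.** Efficiency relative to 10/10 is 4ab/20²:

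- 8/12: 4 × 96/400 = 0.96
- 7/13: 4 × 91/400 = 0.91

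**Do blocks alone help?** A block of 2m patients with known size has on average 2m/(m+1) certain allocations: 4/3 = 1.33 for a block of 4 and 6/4 = 1.5 for a block of 6. Two blocks of each make 20 patients. If sizes and order are known, the total is 2 × 1.33 + 2 × 1.5 ≈ 5.7 certain allocations, more than the 1.82 for one shuffled list.

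**The case against.** The strongest reply is that simple randomisation is loose wording for drawing lots from a set of ten A and ten B. That is plausible, and it would deliver 10/10 with only about 1.8 certain allocations on average. It does not rescue the text: such a list is a restricted scheme, should be named as one, and still leaves the last allocation certain to anyone counting.

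It is also fair to say that unequal groups would do little harm in themselves. Efficiency at 7/13 is still 0.91. If a standardised difference of 1.325 is assumed, chosen to give 80% power at 10/10 with two-sided alpha 0.05, power at 7/13 is about 76%, a loss of about 4 points. The protocol supplies neither the effect size nor the alpha, so this is illustration only. Imbalance is not the main issue.

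Three stronger readings are tempting, and the documents do not support them.

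- A reader might infer that 10/10 can be reached only by closing an arm once it holds 10 patients. A shuffled list reaches it too, so the figure of 3.5 cannot stand alone.
- A reader might infer from the order of headings that patients are allocated before surgery. No time of allocation is stated, and the first arm-specific act is the step 4 blood draw.
- A reader might infer that eligibility is settled only at surgery, so that exclusions after randomisation must follow. Socket class and adequate bone are inclusion criteria, a preoperative CBCT is planned to assess the bone, and no intraoperative eligibility check or withdrawal rule is described.

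**Conclusion.** The point stands. The stated method yields the stated sizes 17.6% of the time; this is exact under independent 1:1 allocation. If 10/10 is enforced and past allocations are tracked, between about 1.8 and 3.5 of the 20 allocations are certain in advance on average, depending on a mechanism that the protocol does not state.

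Two parts are inference. That the team could follow the counts is drawn from the visibly different preparations and the absence of any blinding text. That foreknowledge would change who is enrolled or how they are treated is a risk; the documents do not allow the resulting bias to be quantified. The number of certain allocations is modest, but randomisation is the main safeguard for the comparison this trial exists to make, and later analysis could not reliably undo selective allocation. The missing concealment weighs more than the arithmetic of group sizes.

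**What to change.** In the Randomization section, replace simple randomisation with a named restricted scheme that gives 10/10: either one random list of ten A and ten B, or randomly varying blocks with the sizes withheld from the operating team. Blocks by themselves do not lower predictability; the protection comes from concealment and late opening. Keeping simple randomisation and accepting unequal groups would also be coherent, but the fixed tens would then have to be removed, and concealment would still be needed.

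State that the list is generated in advance by someone not involved in recruitment or surgery, and held in sequentially numbered, opaque, sealed envelopes. Each envelope is opened after implant placement (Surgical Phase, step 3) and immediately before the step 4 blood draw. This fits the surgical order already written, and by then the patient is enrolled and the implant is in position.

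The cost is a short amendment, 20 envelopes and one independent person. The small downside is that both sets of tubes must be ready for each case.
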